Randomized into group (once daily basal insulin, 3x daily rapid acting insulin, or placebo) Insulin (basal or rapid) or placebo, will be supplied by the manufacturer in identical standard insulin vials. Participants will be instructed in subcutaneous injection technique. Study medication adjustments will be made under the supervision of the research teams, who are quite familiar with insulin management in patients with CF, and who will be available at all times for support.

PROTOCOL TITLE: The Impact of Insulin Therapy on Protein Turnover in Pre-Diabetic Cystic Fibrosis Patients

VERSION DATE: 28 June 2021

Visit 3 (Week 6, +/- 7 days): Complete the meal-stimulated protein flux study part again from Phase 1 along with the DXA scan, CFQ-R, and CGM placement. There will not be a dietitian consult at this visit.

Visit 4 (Week 7, +/- 1 day): outpatient blood draw to assess individual proteins and removal of continuous glucose monitor

Visit 5 (Week 8, +/- 1 day): outpatient blood draw to assess individual proteins and end study.

Between Visits:

Study personnel will contact (e.g. telephone, email) patients every three days while insulin is being adjusted and weekly thereafter in addition to their study visits. During these contacts staff will review and adjust (if needed) the medication dose, review hypoglycemia symptoms and management, monitor acute illness or adverse events, provide education, and encourage adherence.

[figure not shown]
Participants will also be asked record their blood glucose levels at random times during the entire study. These need to be recorded to determine clinically if insulin adjustment is necessary.

Patients will receive all usual CF care; study participation will not impact standard-of-care treatment.

PROTOCOL TITLE: The Impact of Insulin Therapy on Protein Turnover in Pre-Diabetic Cystic Fibrosis Patients

VERSION DATE: 28 June 2021

5.3. Study Duration: Each study participant will be in the study for an 8 week duration.

- Anticipated duration to recruit all study participants is 4.5 years.
- The anticipated duration to complete all study procedures, including any long-term follow-up, and data analysis is 5 years.

5.4. Individually Identifiable Health Information: Research participants in this study will sign an Authorization to Use or Disclose Protected Health Information for Research Purposes.

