PROTOCOL TITLE: The Impact of Insulin Therapy on Protein Turnover in Pre-Diabetic Cystic Fibrosis Patients

VERSION DATE: 28 June 2021

8.3. Screening: Screening begins with identification of eligible subjects using the standard OGTT recommended annually for all CF patients. Currently at UMN we have 121 CF patients age 10-25, 58 of whom have IGT or INDET and meet study entrance criteria. Nine new patients per year in this age range are diagnosed with IGT or INDET at UM and thus become eligible for the study. An additional 46 non-diabetic children and youth age 10-25 years are followed at our Children's Hospitals and Clinics of Minnesota CF affiliate, 20 of whom currently have abnormal glucose tolerance. Three to four new patients per year become eligible. Our experience from previous CF studies in this age group suggests ~60% will agree to participate. Over the study period we anticipate that 45-50 CF patients will participate from UM and 10-15 from Children's. Normal control subjects will be recruited from fliers placed in the clinics and the University campus. In addition, siblings of CF participants will be invited to participate as controls. CF subjects will be randomized in a 1:1:1 ratio to basal insulin, pre-meal insulin, or injectable placebo (half 3x/daily pre-meal, half 1x/daily), stratified by 2 age intervals (10-17, 18-25y) and gender. Randomization will be done with computer-generated lists for each strata, in randomly alternating blocks of 3 and 6. The research subject, investigator and clinic personnel will be blinded to assignment. Healthy controls will be matched for gender, age and BMI percentile. The statistician will review control recruitment after every 5 subjects to ensure they are representative of the patient groups and determine whether specific control ages or genders should be recruited.

8.4. Vulnerable Populations:

- Children
- Pregnant women/Fetuses/Neonates
- Prisoners
- Adults lacking capacity to consent and/or adults with diminished capacity to consent, including, but not limited to, those with acute medical conditions, psychiatric disorders, neurologic disorders, developmental disorders, and behavioral disorders
- Approached for participation in research during a stressful situation such as emergency room setting, childbirth (labor), etc.
- Disadvantaged in the distribution of social goods and services such as income, housing, or healthcare

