Analysis of secondary protein turnover endpoints will be exploratory extensions of previous work (37, 38, 57, 58). For the 3 proteins of interest (albumin, transferrin, clusterin), both the fractional synthesis rate and relative isotopic enrichment (ratio of isotopic enrichment to the baseline enrichment) will be calculated from each of the 4 weekly blood samples after both the week 0 and week 8 labeled-infusion studies. At these same points we will also assess the accumulation of damaged proteins, since

PROTOCOL TITLE: The Impact of Insulin Therapy on Protein Turnover in Pre-Diabetic Cystic Fibrosis Patients

VERSION DATE: 28 June 2021

oxidative stress is likely to be reduced during insulin therapy. The baseline (wks 0-4) comparison will be between CF participants and healthy controls, while the comparison of the treatments will use measurements from both weeks 0-4 and 8-12. The profiles of these rate changes over time will be compared visually, by summary measures such as slope if applicable, and by mixed effects linear model for longitudinal trends, with participants treated as a random effect to model the correlation between repeated observations from the same subject.

Protein metabolomics will be assessed during the in-patient studies at week 0 and week 8. The baseline comparison will be between CF participants and healthy controls, while the comparison of the treatments will use changes from week 0 to week 8. The comparison of protein metabolomics will use principal components analysis of the baseline protein and metabolite measurements to find separated clusters of CF participants versus healthy controls, and principal components analysis of the week 8 measurements to compare clusters between the three treatment groups.

Secondary mechanistic endpoints are measured weekly during both baseline and intervention phases: 3-point glucose profiles, mean and MAGE plasma glucose will be measured at weeks 1-12 using CGM. We will use a mixed-effects linear model to compare these longitudinal profiles of plasma glucose between treatments, adjusting for the appropriate baseline value and treating participants as a random effect to model the correlation between repeated observations from the same participant.

The safety analysis will estimate and compare rates of hypoglycemia and subclinical hypoglycemia (identified from CGM) between treatments using Poisson regression. In addition, rates of non-adherence will be compared between treatments.

Power Analysis

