
We anticipate that 45 participants, 15 from each of 3 arms, will provide sufficient power to detect clinically significant improvements in protein turnover (ΔQP and ΔQPT) at baseline, based on comparisons between healthy controls and insulin-insufficient CF patients in our previous study (18). Details are given below. We have inflated the sample size to 20 per arm to allow replacement of drop-outs and non-adherent participants, participants who develop diabetes, or suffer an acute exacerbation. The most common reason for drop out is likely to be acute illness, although the brief (3 month) time span will help reduce this. Also, given the short time span of this study we anticipate adherence will be good. This is in line with other studies in CF where about 80% of subjects are adherent at least 80% of the time (24, 65). Because many of our subjects will be adolescents, one might expect somewhat worse adherence. However, we believe this will be offset by the short duration of the study and by mechanisms to encourage adherence such as school nurse supervision on school days and frequent contact with study personnel. Study drop-out may occur due to development of fasting hyperglycemia or acute illness. These are discussed in greater detail in the human

PROTOCOL TITLE: The Impact of Insulin Therapy on Protein Turnover in Pre-Diabetic Cystic Fibrosis Patients

VERSION DATE: 28 June 2021

subjects section. We expect less than 2% of subjects to develop CFRD during the 3 month study period. Patients who experience acute illness during the study may repeat it when they are well. Thus, we have inflated our group size to account for 20% non-adherence, 1-2% development of diabetes, and 11-12% acute illness.

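### The Poisson comparison of CGM-detected hypoglycemia makes no allowance for participants having different event rates and states no exposure offset

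*Combined protocol and SAP*

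**What the plan says.** The formal hypoglycemia comparison is one sentence in Section 14 (Statistical Considerations): "The safety analysis will estimate and compare rates of hypoglycemia and subclinical hypoglycemia (identified from CGM) between treatments using Poisson regression". Neither that section nor any other gives the unit of analysis, an exposure offset, or a way of handling extra-Poisson variation (scale factor, negative binomial model, robust variance or participant effect).

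The paragraph before it, on CGM glucose profiles, does deal with dependence. It specifies a mixed-effects linear model, "treating participants as a random effect to model the correlation between repeated observations from the same participant". That provision is written for the glucose model only.

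The monitored period is described in two ways. Section 14 says "mean and MAGE plasma glucose will be measured at weeks 1-12 using CGM". Section 5.2 places the monitor at Visit 3 (week 6, within 7 days either side) and describes Visit 4 (week 7) as "outpatient blood draw to assess individual proteins and removal of continuous glucose monitor", which is about one week on treatment. Section 5.3 has each participant in the study for 8 weeks.

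The only event information is in Section 16.2: no severe episode among the 24 subjects studied so far. No rate or between-participant variance is given for milder or CGM-detected events.

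**The concern.** A Poisson model takes the variance of a participant's count to equal its mean. Within an arm that holds if everyone shares one underlying rate and episodes occur independently. Several features of this trial make a common rate hard to assume for CGM-detected events. Doses are individually reviewed and adjusted (Section 5.2). The sample size allows for 20% non-adherence (Section 14). Ages run from 10 to 25, and two categories of abnormal glucose tolerance are eligible (Section 8.1). If rates differ for these reasons, counts spread more widely than Poisson allows and the reported intervals are too narrow.

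What is at stake is the safety half of Hypothesis 2, which claims that once-daily basal insulin is safe as well as equally beneficial. This sentence is the only formal comparison of hypoglycemia between regimens and against placebo. Intervals that are too narrow can show a difference that is not there, and can also make an apparent similarity look better established than it is.

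**Working it through.** **Inputs from the documents.** The model is Poisson regression (Section 14). Allocation: "CF subjects will be randomized in a 1:1:1 ratio to basal insulin, pre-meal insulin, or injectable placebo" (Section 8.3). Evaluable size: "We anticipate that 45 participants, 15 from each of 3 arms, will provide sufficient power". Planned size: "We have inflated the sample size to 20 per arm" (both Section 14). The plan states no rate, dispersion, significance level or power for this comparison, so there is no figure of its own to reproduce.

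**Assumptions.** Two-sided 5% for each pairwise contrast; equal true rates in the two arms compared; equal monitored time; gamma-distributed participant rates. The mean count per participant (mu) and the between-participant variation (k) are assumed and varied.

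**Formulas.**
- Variance of a participant's count = mu + k·mu², so variance/mean ratio V = 1 + k·mu.
- The true standard error of the log rate ratio is √V times the Poisson one.
- Approximate false-positive rate of a nominal 5% Wald test = 2[1 − Φ(1.96/√V)].

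For V = 2: √2 = 1.41, 1.96/1.41 = 1.386, and 2[1 − Φ(1.386)] = 16.6%.

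**Results.** The simulated column uses 20,000 trials per setting, 15 or 20 per arm and 1 to 4 events per participant.

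| V (assumed) | True SE / Poisson SE | Formula | Simulated Poisson Wald |
|---|---|---|---|
| 1 | 1.00 | 5.0% | about 5% |
| 1.5 | 1.22 | 11.0% | 10-11% |
| 2 | 1.41 | 16.6% | 15-17% |
| 3 | 1.73 | 25.8% | 24-25% |
| 5 | 2.24 | 38.1% | 35-38% |

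The number per arm does not appear in the formula, and the results at 15 and 20 are nearly the same. More participants would not cure the problem. Over the same settings, Pearson-scaled Poisson with a t reference rejects 2.8-5.2% of the time.

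**Where the effect is absent.**
- *Repetition alone (k = 0).* With 15 per arm and 1 to 20 events per participant, the Poisson Wald test rejects 4.5-5.0% of the time. Repeated events do no harm when all participants share one rate.
- *Rare events (mu = 0.1).* Even at k = 2, V = 1 + 2 × 0.1 = 1.2 and √1.2 = 1.10. Wald false positives are at most 0.2%. The difficulty here is sparse data. With a common rate, an arm of 15 has no events with probability exp(−15 × 0.1) = exp(−1.5) = 22%, and an arm of 20 with probability exp(−2) = 14%. A finite log rate ratio then cannot be estimated, with or without scaling.

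**Why the window matters.** For a stable participant rate, mu grows with monitored time, and so does k·mu. As an illustration with assumed values, take 0.5 events per week and k = 1. One monitored week gives V = 1 + 0.5 = 1.5. The six treatment weeks of Section 5.1 give mu = 3 and V = 4, for which the formula gives 2[1 − Φ(0.98)] = 33%, against 11%. The two CGM descriptions therefore imply different exposures and different sensitivity to the choice of model.

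**The case against.** The strongest reply is that the text is silent rather than wrong. Poisson regression is routinely fitted with a scale factor, robust variance or offset, and Section 14 excludes none of these. It also speaks of rates, which implies a denominator. This stands in part: a reader might infer that the plan prescribes an unadjusted model, and the documents do not say so. But the plan spells out a participant effect for the neighbouring glucose model and not here, so an analyst following the text could reasonably fit the ordinary model.

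A reader might also infer that repeated events in one patient are themselves the fault, and that false safety signals are likely. The documents do not support either. Repetition at a common rate is harmless, as shown above. Likelihood depends on a rate and a dispersion that appear nowhere in the documents. The rejection rates follow almost entirely from the assumed ratio, so the simulation shows how sensitive the test is and is not evidence about this trial. At a ratio near 1 the plan would be adequate.

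A third tempting inference is that the severe hypoglycemia comparison is compromised, because Section 16.2 names that as the main risk. With no severe episode in 24 subjects, it is the endpoint least affected by overdispersion.

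Finally, this is a secondary analysis with no stated significance level or decision rule, and safety oversight runs through monthly adverse-event review (Section 16.2). That limits the consequence to the reported intervals and p-values and to what is concluded about safety under Hypothesis 2.

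**Conclusion.** The concern holds in a conditional form and mainly for CGM-detected subclinical events. Section 14 makes no allowance for between-participant variation and states no exposure offset. If participants' rates differ or episodes cluster, which is plausible here, Poisson intervals are too narrow. Even a mild variance/mean ratio of 1.5 roughly doubles the nominal 5% error, and a ratio of 5 takes it to 35-38%. If the ratio is 1, nothing is lost.

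These sizes rest on assumed ratios, 1 to 4 events per participant, equal monitored time and a two-sided 5% test. None of these is in the documents except the 15 to 20 participants per arm. The documents do not support a claim that the analysis is wrong as written, or that rare clinical or severe events are materially affected. The appropriate label is a cheap improvement.

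**What to change.** First reconcile the CGM windows in Sections 14 and 5.2, because the offset cannot be defined until the monitored period is. Section 14 should also say what counts as one episode.

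Then replace the sentence in Section 14 along these lines:
- For CGM-detected events, analyse one count per participant with log(monitored time) as offset, by Pearson-scaled (quasi-)Poisson regression with a t reference.
- Report the estimated dispersion.
- Use negative binomial regression as a sensitivity analysis.
- For clinical events, if counts are sparse or an arm has none, report counts and exact rate intervals in place of a modelled rate ratio.

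Other choices, such as negative binomial regression as the main model, would also answer the point. Robust standard errors would too, but at 15 or 20 per arm they were slightly liberal with strong between-participant variation (up to 7.8% false positives). Scaled Poisson stayed between 2.4% and 5.3% for means of 0.5 to 20 events per participant and k from 0 to 2.

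The cost is a short edit to Section 14, plus the reconciliation of the windows, and no new data. The downside is wider intervals when overdispersion is present. When it is absent, almost nothing is lost.

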To conduct a double-blind, placebo-controlled study of the impact of daily insulin therapy on meal stimulated protein turnover in 60 youth age 10-25 years with CF and abnormal glucose tolerance. Assessment will occur before and after 1 month of insulin therapy.

Hypothesis 1: In this insulin insufficient CF population, daily insulin replacement therapy will reduce meal stimulated protein catabolism from pre-insulin baseline, and will produce greater reductions from baseline than in placebo-treated patients.

Specific Aim 2

To ascertain differences in the impact of 1X daily basal insulin versus 3X daily rapid-acting insulin on meal stimulated protein turnover in 60 youth age 10-25 years with CF and abnormal glucose tolerance.

Hypothesis 2: A single daily dose of basal insulin will safely provide the same therapeutic benefit as the current standard method of insulin delivery of pre-meal 3x daily rapid acting insulin.

Specific Aim 3

In a novel exploratory aim, we will assess the turnover of 3 individual proteins previously implicated in CF pathophysiology--- albumin, transferrin, and clusterin--- to determine the extent to which their synthesis and accumulation differs at baseline from normal controls and is subsequently affected by insulin therapy. Twenty matched healthy controls will be assessed at baseline only (no insulin therapy).

2. Background

2.1. Significance of Research Question/Purpose: Given the universal prevalence of insulin insufficiency in CF, the high lifetime risk of developing diabetes, the clinical impact of insulin insufficiency on protein catabolism and survival in CF, and the critical importance of maintaining body weight and LBM in this population, there is an urgent need to determine whether insulin replacement therapy should be instituted for anabolic purposes prior to the actual onset of diabetes and, if so, to ascertain the optimal regimen.

PROTOCOL TITLE: The Impact of Insulin Therapy on Protein Turnover in Pre-Diabetic Cystic Fibrosis Patients

VERSION DATE: 28 June 2021

2.2. Preliminary Data: In a placebo-controlled clinical trial, insulin therapy improved body mass index (BMI) and LBM in patients with very early CFRD (CFRD without fasting hyperglycemia), and this is now standard care for these patients.

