- Serious health condition for which there are no satisfactory standard treatments
- Fear of negative consequences for not participating in the research (e.g. institutionalization, deportation, disclosure of stigmatizing behavior)

PROTOCOL TITLE: The Impact of Insulin Therapy on Protein Turnover in Pre-Diabetic Cystic Fibrosis Patients

VERSION DATE: 28 June 2021

- Any other circumstance/dynamic that could increase vulnerability to coercion or exploitation that might influence consent to research or decision to continue in research
- Undervalued or disenfranchised social group
- Members of the military
- Non-English speakers
- Those unable to read (illiterate)
- Employees of the researcher
- Students of the researcher
- None of the above

8.5. Additional Safeguards:

Given the universal prevalence of insulin insufficiency in CF, the high lifetime risk of developing diabetes, the clinical impact of insulin insufficiency on protein catabolism and survival in CF, and the critical importance of maintaining body weight and LBM in this population, there is an urgent need to determine whether insulin replacement therapy should be instituted for anabolic purposes prior to the actual onset of diabetes and, if so, to ascertain the optimal regimen. The current protocol describes a double-blind, placebo-controlled trial to determine whether insulin therapy improves protein catabolism in youth with CF and abnormal glucose tolerance, and to explore differences in efficacy between multiple daily pre-meal insulin dosing (as is currently standard for early CFRD) versus a more convenient once daily basal insulin dose (as has been used in small uncontrolled pilot studies). The findings of this study will provide a mechanistic rationale for instituting insulin in youth with CF and pre-diabetes, and will inform both research studies and clinical practice as to the best regimen for insulin delivery in this population.

Both parents must give their permission unless one parent is deceased, unknown, incompetent, or not reasonably available, or when only one parent has legal responsibility for the care and custody of the child.

The minor will be able to give assent and if he/she chooses not to participate, the choice will be honored.

9. Local Number of Participants

9.1. Local Number of Participants to be Consented: We have consented 40 CF patients, and need 30 control patients in total.

10. Local Recruitment Methods

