The protein turnover portion of the study will only be done at the University of Minnesota where the staff have the necessary expertise to perform these complicated medical studies. [name] is in regular (at least monthly) communication with [name] at the University of Iowa to ensure all other study procedures are handled in a consistent fashion. In order to ensure the validity of subject characteristics that may impact the rigor of the study, we will continue to work to make sure we have approximately equal gender distribution and that we have a similar number of pediatric (age 10-18) and young adult (age 19-15) subjects. In order to ensure robust and unbiased results, we are working with collaborators in Italy who are considered the world experts in metabolic mathematical modeling. We send them the raw mass spectroscopy data and they perform the mathematical analysis. They are blinded to treatment arm, which will help ensure the validity of the data.

16.2. Data Safety Monitoring.

In addition to the two study visits, the study nurse coordinator is in weekly contact with study participants and all adverse events are recorded on case report forms. The safety data including all adverse events are reviewed monthly by the investigators. The only significant potential risk directly associated with this study is that of severe hypoglycemia, if the insulin dose is too high for the subjects. In fact, we have now studied 24 subjects and have not had one single episode of severe hypoglycemia, so the risk is low. The only adverse events that have occurred are respiratory infections as is expected in cystic fibrosis. The investigators are all pediatric endocrinologists, well experienced with insulin administration and management of hypoglycemia. Efficacy data will not be reviewed until study end. No conditions have been identified that would trigger an immediate suspension of the research.

17. Provisions to Protect the Privacy Interests of Participants

17.1. Protecting Privacy: Your records will be kept private. [name] will keep the study data and your name on her password-protected desktop computer kept in her secure UM office. No one outside of [name] and the research team will have access to your name or identifying information. All samples sent to the Mayo Clinic will not have any information from which you could be identified. In any publications or presentations, we will not include any information that will make it possible to identify you as a

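### No interval or bound backs the safety claim in Hypothesis 2, and Poisson regression may give no usable rate ratio if clinical hypoglycemia is rare

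*Combined protocol and SAP*

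**What the plan says.** Hypothesis 2 (Section 1, Specific Aim 2) includes a safety claim: "A single daily dose of basal insulin will safely provide the same therapeutic benefit" as pre-meal rapid-acting insulin. Section 14 gives one sentence on how safety will be compared: "The safety analysis will estimate and compare rates of hypoglycemia and subclinical hypoglycemia (identified from CGM) between treatments using Poisson regression". It adds that non-adherence rates will be compared. It states no interval, acceptable upper limit, expected rate, event definition or method for sparse counts.

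The sample size was set on protein turnover: "We anticipate that 45 participants, 15 from each of 3 arms", then "We have inflated the sample size to 20 per arm" to cover losses. The 80% power in the Section 14 table refers only to those endpoints.

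On experience so far, Section 16.2 says "we have now studied 24 subjects and have not had one single episode of severe hypoglycemia", and concludes from this that the risk is low. It also says: "The only adverse events that have occurred are respiratory infections as is expected in cystic fibrosis".

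**The concern.** The protocol states safety as part of a hypothesis but defines no result that would support or refute it. A plain between-arm comparison then invites the reader to take no significant difference as safe. That inference is weak when events are few, and Section 16.2 already reasons in a similar way from zero severe episodes.

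There is also a technical problem. If an arm has no clinical events, the fitted log rate ratio runs off to infinity and the usual output cannot be used. The participants are aged 10 to 25 and do not have diabetes, and Section 1.1 expects the findings to inform practice. A safety statement should therefore show how large an excess of hypoglycemia remains compatible with the data.

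**Working it through.** **The plan's own figures.** No safety power is stated, so there is none to reproduce. The protein turnover table can be checked. SD of change = 4.0 × √(2(1 − 0.6)) = 3.58 for QP, and 1.26 × √0.8 = 1.13 for QPT. A two-sided 5% two-sample t test at 80% power gives minimum differences of 3.79 and 3.25 (QP), and 1.19 and 1.02 (QPT), for 15 and 20 per group. The table shows 3.8, 3.3, 1.2 and 1.0. Two-sided 5% is therefore used below, although the plan does not state it.

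**What zero in 24 shows.** The one-sided 95% upper limit is 1 − 0.05^(1/24) = 11.7%. This pools everyone studied. If 16 had received insulin (an assumption; the number is not given), it would be 1 − 0.05^(1/16) = 17.1%.

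**A zero-event arm, 20 per arm, equal exposure.** With 0 v b events, the likelihood-ratio statistic is 2b ln 2 and the exact conditional two-sided p is 2 × 0.5^b.

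| Events | Wald p | Likelihood-ratio p | Exact p |
|---|---|---|---|
| 0 v 3 | 0.999 | 0.041 | 0.25 |
| 0 v 5 | 0.999 | 0.008 | 0.06 |
| 0 v 8 | 0.999 | 0.0009 | 0.008 |

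At 0 v 8 the Wald standard error is about 15,600, an artefact of where the fitting stops. The Wald test hides a clear excess at 0 v 8, while the likelihood-ratio test declares one at 0 v 3 that the exact test does not support. Robust standard errors do not help: at 0 v 5 they give SE 0.39 and p near 0, against exact 0.06. In every row the ratio estimate is infinite.

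**How likely is a zero arm?** With m reference-arm events per participant and a true ratio of 2, the chance that at least one of the two arms has no events is 1 − (1 − e^(−nm))(1 − e^(−2nm)). For 15 / 20 per arm:
- m = 0.05: 59% / 45%
- m = 0.1: 26% / 15%
- m = 0.25: 2.4% / 0.7%

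The problem is confined to rare events.

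**Power for a doubled rate.** Reference-arm events needed = (z_α + z_β)² × (1 + 1/2) / (ln 2)².
- 80% power: (1.960 + 0.842)² × 1.5 / 0.480 = 24.5, so about 25 events. This is 1.6 per participant with 15 per arm, or 1.2 with 20.
- 50% power: 1.960² × 1.5 / 0.480 = 12.0 events, or 0.8 and 0.6 per participant.

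The chance of missing a doubling over the 6-week treatment period (6 × 12/52 = 1.38 months), at assumed reference rates:

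| Events per patient-month | Wald, 15 / 20 per arm | Exact, 15 / 20 per arm |
|---|---|---|
| 0.1 | 98% / 95% | 95% / 92% |
| 0.2 | 85% / 77% | 86% / 80% |
| 0.5 | 55% / 43% | 61% / 48% |
| 1.0 | 25% / 14% | 28% / 16% |
| 2.0 | 4% / 1% | 4% / 1% |

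These are plain Poisson figures. Between-patient overdispersion, once properly allowed for, lowers power further.

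**What an interval gives instead.** With no events among 20 participants, the exact two-sided 95% upper limit is −ln(0.025)/20 = 0.18 events per participant. This is a usable statement where the ratio is not.

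**The case against.** Five points can fairly be made for the plan.

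- **No rate is given.** A reader might infer that the planned analysis would miss a doubled rate in most plausible cases. The documents do not support that. At 2 events per patient-month the miss rate is only 4% or 1%, and CGM-identified events could well be that frequent. This objection stands.
- **The p near 1 is a Wald result, and the plan names no test.** This is true: a likelihood-ratio test from the same model rejects at 0 v 8. But that test is too liberal at 0 v 3, and the ratio is not finite under either.
- **An exact test does not cure low power.** This is also true, as the last table shows. With a zero-event reference arm, the exact ratio has no finite upper limit either. The limit comes from the number of events, so the remedy has to be an interval and a decision rule.
- **Nothing says that non-significance will be read as safe.** Section 14 promises to estimate rates as well as compare them, and Section 1.1 speaks of exploring differences in efficacy between the regimens. The misreading is therefore a risk and not a stated intention. Still, Hypothesis 2 makes the claim and nothing else in the plan defines how it will be judged.
- **Sparse clinical events are an inference.** Section 16.2 does not say how many of the 24 received insulin, whether controls are among them, or whether mild episodes were logged. A reader might derive an event rate from those 24, but it would rest on a guess.

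**Conclusion.** The point holds in a limited form. The safety claim in Hypothesis 2 has no interval or bound behind it. For rare clinical hypoglycemia, standard Poisson output can fail: there is no finite ratio if an arm has no events, and p-values are unreliable in both directions. Whether this happens depends on an event rate that the plan does not give. A zero arm is a live risk at about 0.1 events per participant or fewer, and negligible from 0.5 upward. A doubling is missed more often than not below about 0.6 (20 per arm) to 0.8 (15 per arm) events per participant.

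The figures assume two-sided 5%, equal exposure and no overdispersion. The conclusion that a non-significant comparison cannot support the safety claim does not depend on the rate: the plan sets no limit against which such a result could be judged. This is a cheap improvement, not a flaw in the primary analysis.

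**What to change.** In Section 14:

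1. For clinical hypoglycemia, report each arm's rate with an exact Poisson interval.
2. Report basal v pre-meal, and each insulin arm v placebo, as rate differences and rate ratios with 95% limits from a method that tolerates zero events (exact conditional, profile-likelihood or penalised). If the reference arm has no events, rely on the difference.
3. Keep the Poisson-type model for the more frequent CGM-identified events. Define the events and the exposure time. The CGM windows need to be reconciled first: Section 5.2 has on-treatment CGM from week 6 to week 7, Section 14 has weeks 1 to 12, and Section 5.3 gives an 8-week study.
4. State that a non-significant comparison will not be reported as evidence of safety. Judge the safety part of Hypothesis 2 on the upper limit of the rate difference against a bound chosen by the investigators. If they set none, call the safety analysis descriptive and do not present safety as a tested claim.

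The cost is some wording and a few lines of code, with no new data or participants. The downside is a more cautious safety conclusion, because the limits will be wide at 15 to 20 per arm.
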